### 7.2.3 Post 6MWT

Post each 6MWT, participants will record

- Respiratory rate
- Pulse (beats per minute)
- Post-walk dyspnea and fatigue levels measured by the Modified Borg scale

Before the next 6MWT, participants will rest for at least 1 hour breathing their supplemental oxygen device prior to switching to the alternate device for the second test.

After each of the two 6MWTs, participants will complete a participant acceptance questionnaire involving questions about ease of use and other aspects specific to portable oxygen use.

## 7.3 End of Study

End of study is considered to be the completion of Visit 1. There is no follow up period.

## 8. Adverse Events

### 8.1 Definitions

#### 8.1.1 Adverse Event

Any untoward medical occurrence, unintended disease or injury or any untoward clinical signs in participants, whether or not related to the investigational medical device.

An AE includes:

- A clinically significant worsening of a pre-existing condition.

The following should **not** be reported as AEs:

- Pre-existing conditions, including those found as a result of screening or other study procedures performed before exposure to study product (pre-existing conditions should be reported as medical history or concomitant illness).
- Pre-planned procedures, unless the condition for which the procedure was planned has worsened from the first study related activity after the participant has signed the informed consent.

The following three definitions are used when assessing an AE:

- **Severity**
  - **Mild** - no or transient symptoms, no interference with the participant's daily activities.
  - **Moderate** - marked symptoms, moderate interference with the participant's daily activities.
  - **Severe** - considerable interference with the participant's daily activities; unacceptable.
- **Causality**

Relationship between an AE and device(s):

  - **Unrelated:** The event is due to the underlying disease state or concomitant medication or therapy not related to the study-specific devices or procedures.
  - **Unlikely related:** The event had no significant temporal relationship to the study-specific devices or procedures and/or a more likely alternative etiology exists.
  - **Possibly related:** The event had a strong temporal relationship to the study-specific devices or procedures and alternative etiology is equally or less likely compared to the potential relationship to the study-specific devices or procedures.
  - **Probably related:** The event had a strong temporal relationship to the study-specific devices or procedures and another etiology is unlikely.
  - **Unknown:** Relationship of the event to the study-specific devices or procedures and alternative etiology is unknown
- **Final outcome**
  - **Recovered/resolved** - The participant has fully recovered, or by medical or surgical treatment the condition has returned to the level observed at the first study -related activity after the participant signed the informed consent.
  - **Recovering/resolving** - The condition is improving and the participant is expected to recover from the event. This term is only applicable if the participant has completed the study or has died from another AE.

- **Recovered/resolved with sequelae** - The participant has recovered from the condition, but with lasting effect due to a disease, injury, treatment or procedure. If a sequelae meets an SAE criterion, the AE must be reported as an SAE.
- **Not recovered/not resolved** - The condition of the participant has not improved and the symptoms are unchanged, or the outcome is not known.
- **Fatal** - This term is only applicable if the participant died from a condition related to the reported AE. Outcomes of other reported AEs in a participant before he/she died should be assessed as “recovered/resolved”, “recovering/resolving”, “recovered/resolved with sequelae” or “not recovered/not resolved”. An AE with fatal outcome must be reported as an SAE.
- **Unknown**

### 8.1.2 Serious Adverse Event

A serious adverse event is an adverse event that:

- Leads to death, or
- Leads to serious deterioration in the health of a participant that:
  - results in a life-threatening illness or injury,
  - results in permanent impairment of a body structure or body function,
  - requires inpatient hospitalization or prolongation of existing hospitalization,
  - results in medical or surgical intervention to prevent permanent impairment to a body structure or a body function.
- Leads to fetal distress, fetal death or a congenital abnormality or birth defect.

### 8.1.3 Anticipated Adverse Events

Warnings, contraindications, and hazards are outlined in the User Manual for Mobi™ and should be reviewed with participants when they receive their study devices. All study devices are to be used in accordance with their respective approved, current instructions found in the manual. Anticipated adverse events include events that are reasonably expected to occur as a result of the participant’s disease state or treatment.

#### 8.1.3.1 COPD-related Anticipated Adverse Events:

- COPD exacerbation and related symptoms anticipated during this study include:
  - Cough
  - Dyspnea (shortness of breath)
  - Excessive mucus production
  - Wheezing
  - Chest tightness
  - Cyanosis
- Lack of energy (fatigue)

#### 8.1.3.2 LTOT-related Anticipated Events:

Adverse events associated with LTOT during this study include, but are not limited to, the following:

- Nosebleed
- Dry mouth
- Dry throat
- Headache

- Tripping/falling over equipment
- Noise irritation

## **8.2 Adverse Event Assessment and Reporting**

### **8.2.1 Adverse Event Assessment**

Adverse event information will be collected on all participants. At every participant encounter throughout the study, the investigator will inquire about adverse events since the last encounter.

### **8.2.2 Adverse Event Reporting**

Adverse events (AEs) are to be reported in the electronic study database on an AE eCRF as soon as possible after discovery by the site and are to be updated with new information and upon final resolution of the event. Supporting source documents for SAEs may be requested; if requested, these documents are to be de-identified, labeled with the participant number, and an email will be promptly provided or uploaded to the electronic study database. Adverse events will be evaluated by the investigator and classified for seriousness (as defined in Section 8.1.2), relatedness, and severity.

### **8.2.3 For US only: Mandatory Medical Device Reporting**

Manufacturers are required to report to the FDA via an electronic equivalent of Form 3500A when they learn that any of their devices may have caused or contributed to a death or serious injury or has malfunctioned and the malfunction would be likely to cause or contribute to a death or serious injury if it were to recur (key terms are defined in 21 CFR 803.3.). Manufacturers must also report to the FDA when they become aware that their device has malfunctioned and would be likely to cause or contribute to a death or serious injury if the malfunction were to recur. Should such an event occur during this study, the appropriate device manufacturer will file Form 3500A with FDA's Center for Devices and Radiological Health as required by law.

### **8.2.4 Device Deficiency**

Inadequacy of a medical device related to its identity, quality, durability, reliability, safety or performance, such as malfunction, misuse or use error or inadequate labelling.

The investigator shall record every Device Deficiencies with assessment on the study Case Report Forms (CRF) (paper or electronic).

All Device Deficiencies assessed by the investigator that may have led to (had the potential to lead to) an SAE, if appropriate action had not been taken, intervention had not occurred, or circumstances had been less fortunate are treated as the same reporting category as SAEs and must be reported accordingly to the SAE process

## **9. Risk and Benefits**

### **9.1 Potential Risks**

Refer to Section 8.1.3 for a list of potential risks.

#### **9.1.1 Minimization of Risks**

This study involves the use of a FDA-cleared, Class II medical device and CE marked devices that deliver oxygen therapy with no greater than minimal risk to participants. All study devices will be used in accordance with their respective approved indications and instructions.

As per FDA good practice guidelines (21 CFR 10.115), this study protocol as well as the Mobi™ device was assessed for risk to participants. As this study does not meet the definition of significant risk as defined by 21 CFR 812.3(m), the investigative team has determined that this protocol and the Mobi device is non-significant risk. All participants will maintain all other therapy regimens per standard clinical care; this protocol does not dictate any other adjustments to the participants' care regimen and there are no protocol-required assessments or procedures that pose significant risk to the participants. As required by the FDA, the IRB will review this study protocol and make the final determination of NSR designation.

Participants should be encouraged to discuss any issues they are having with therapy during the study. The investigator should assess for changes in the health or well-being of the participant in response to general, non-directed questioning (e.g., "How are you feeling while using the therapy?"). Side effects should be documented on the site's source documents. Furthermore, if during the evaluation the participant cannot complete an assessment, the participant may sit down until they feel stable to continue. Potential expected adverse events are believed to be mild and similar to other commercially available POC systems.

The attending study staff have experience setting up the eligible patient population in this study. All participants return to their current oxygen therapy after completing the study visits. The following will be performed to minimize risks:

#### **9.1.1.1 Safety assessments**

During this study, participants SpO2 and heart rate will be monitored before, during and immediately following the walk to ensure devices connectivity and to ensure participant safety.

#### **9.1.1.2 Site staff training and experience**

A delegated site staff will be present during each session with participants. A delegated site staff should be certified in cardiopulmonary resuscitation with a minimum of Basic Life Support by an American Health Association–approved cardiopulmonary resuscitation course. Advanced cardiac life support certification is desirable. Training, experience, and certification in related health care fields (registered nurse, registered respiratory therapist, certified pulmonary function technician) are also desirable.

#### **9.1.1.3 6MWT guidelines compliance**

6MWTs will be conducted according to the guidelines (ERS/ ATS) and participants will be followed by a delegated site staff. Safety check points for immediately stopping a 6MWT in ERS/ ATS guideline will be undertaken to minimize risk associated with this test. A delegated site staff must recognize these problems and the appropriate responses. If in their clinical judgment there are signs of participant distress, the test session will be stopped and participants will be returned to their current oxygen device.

## **9.2 Potential benefits**

There may be no benefits to participants from taking part in the study. Benefits during the study may include:

- Symptomatic relief from dyspnea.
- Maintenance of SpO2 during 6MWTs.

However, it is not expected that these benefits will last longer than the duration of the study.

## 10. Statistical Considerations

### 10.1 Primary Objective and Endpoint

The primary endpoint is mean SpO2 measured during a 6 Minute Walk Test (6MWT). The primary aim of this protocol is to show non-inferiority between the Mobi oxygen device and the control device with respect to mean SpO2 during the 6MWT.

The null and alternative hypothesis is based on a one-sided non-inferiority test using a non-inferiority margin (NIM) of 2%.

H0:  $\mu_A - \mu_B \leq -\text{NIM}$  (Mobi is inferior)

H1:  $\mu_A - \mu_B > -\text{NIM}$  (Mobi is non-inferior)

where  $\mu_A$  and  $\mu_B$  are the mean SpO2 after using the Mobi device (A) and the Control device (B), respectively, and NIM equals the non-inferiority margin. A significant level of 0.025 will be used.

### 10.2 Analysis Populations

The populations are defined as follows.

- The Intent-To-Treat (ITT) is defined as all patients who meet the inclusion/exclusion criteria and begin the first 6MWT.
- The Completed Cases (CC) population is defined as all patients in the ITT population who complete both the first and second 6MWTs.

The primary endpoint analysis will be based on the CC participant population. A participant may rest during the 6MWT and still complete the test, however if the participant stops completely then the 6MWT will be considered incomplete. A sensitivity analysis of the primary endpoint will be generated for the ITT population. The ITT population may contain some participants who complete the first study 6MWT but not the second study 6MWT. This will require the use of imputation methods for missing values which are documented in Section 10.9.

All safety analyses will be generated for participants in the ITT population. All secondary endpoints will be generated using the CC population.

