#### 7.2.1.1 Oxygen titration

Each participant will undergo titration using Mobi™ to reach SpO2 of  $\geq 90\%$ . After the Mobi™ titration, each participant will rest for at least 1 hour while breathing their supplemental oxygen device to obtain resting SpO2 levels. Participants shall have a resting SpO2 of  $\geq 90\%$  prior to starting each 6MWT.

During use of the oxygen cylinder 6MWT, the settings will be based on the patient's original prescription.

During the use of the Mobi™ device 6MWT, the patient will use Mobi™ based on the titrated Mobi™ setting.

After starting therapy, the site staff should also wait for approximately 5 minutes to make sure no alarms turn on. Both of these oxygen system settings will be recorded.

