### 10.8 Safety Analyses

A listing of all adverse events occurring during the study period will be generated including all participants in the ITT population. The listing will include the event description, time of occurrence, severity, outcome and action taken.

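### The safety set is narrower than device exposure: the adverse event listing leaves out participants titrated on Mobi who never begin a walk, or who are judged ineligible after using a device

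*Combined protocol and SAP*

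**What the plan says.** Section 10.2 (Analysis Populations) defines two sets. The ITT set "is defined as all patients who meet the inclusion/exclusion criteria and begin the first 6MWT", and the Completed Cases set is the part of ITT that completes both walks. No separate safety or as-exposed set is defined. On safety, the section is explicit: "All safety analyses will be generated for participants in the ITT population".

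Section 10.8 (Safety Analyses) plans one output: "A listing of all adverse events occurring during the study period will be generated including all participants in the ITT population".

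Section 7.2.1.1 (Oxygen titration) describes what happens before the first walk. "Each participant will undergo titration using Mobi™ to reach" an SpO2 of at least 90%. After that, "each participant will rest for at least 1 hour while breathing their supplemental oxygen device". A resting SpO2 of at least 90% is to be met "prior to starting each 6MWT". The section also has a device check before walking: "After starting therapy, the site staff should also wait for approximately 5 minutes to make sure no alarms turn on".

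Section 8.2.1 collects AE information on every participant, and section 8.2.2 enters AEs on an AE form in the study database. Neither is restricted to ITT.

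**The concern.** A safety set should contain everyone who was exposed. Here it needs two further things: the participant must satisfy the eligibility criteria, and must have started the first walk. Mobi is used before that walk, so there is a window in which a participant has been on the device under study but is not yet in the safety set.

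The filter need not act at random. An AE during titration or before the walk is itself a plausible reason for not starting. A participant who tolerated the device poorly could thus be one whose events the listing leaves out. A reader of the study report would reasonably take the listing as complete for everyone who used a study device.

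**Working it through.** The point rests on how the definitions fit together, not on a figure.

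**1. Order of events at Visit 1.** By sections 7.2 and 7.2.1.1, an eligible participant is randomized, titrated on Mobi, rests for at least 1 hour, is started on the device for the walk with a check of about 5 minutes, and then walks. Membership of ITT begins only at the last step. Exposure to Mobi begins at titration.

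**2. Participants by type.** Applying 8.2.1, 10.2 and 10.8 as written:

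| Participant | AEs recorded (8.2.1, 8.2.2) | In ITT (10.2) | In the AE listing (10.8) |
|---|---|---|---|
| Eligible, titrated, begins first walk, completes both | Yes | Yes | Yes, including AEs before the walk |
| Eligible, titrated, begins first walk, does not do the second | Yes | Yes | Yes, including AEs before the walk |
| Eligible, titrated, does not begin a walk | Yes | No | No |
| Used one or both devices, judged not to have met the criteria | Yes | No | No |

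The last two rows are the gap. It is a gap by participant, not by time window: the listing covers the study period, so an AE during titration is listed for anyone who goes on to walk.

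**3. Routes into the third row.** Section 11.1.3 lets participants withdraw at any time, and an AE before the walk could stop the visit. Not meeting the resting SpO2 condition is a possible third route, although 7.2.1.1 does not say what follows if it is not met.

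**4. The plan's own idea of exposure.** Section 8.1.1 separates AEs from pre-existing conditions by whether a condition was found before exposure to study product. Starting a walk plays no part there. Section 9.1.1.1 monitors SpO2 and heart rate before the walk for safety. Several events anticipated in 8.1.3.2, such as nosebleed, dry mouth and headache, do not need a walk. Section 10 is therefore narrower than sections 8 and 9.

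**5. Size.** Section 6.1 plans 32 randomized. One participant outside the listing is 1/32 = 3.1% of them. The documents give no rate of loss between titration and the first walk, of ineligibility found after device use, or of AEs in either group, so no expected count or probability is calculated here.

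**6. Effect on the rest of the plan.** The sample size reproduces: SD of the difference = √(3.5² + 2.2² − 2 × 0.2 × 3.5 × 2.2) = √14.01 = 3.74. With 30 participants, a margin of 2 and a one-sided level of 0.025, power from the noncentral t distribution (28 degrees of freedom) is 80.7%. Allowing for drop-out, 30/0.95 = 31.6, rounded up to 32. No input to this calculation depends on the safety set.

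**The case against.** The case for leaving the text alone has several parts.

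- **Nothing is lost from the record.** This stands. AEs are collected and entered for all participants, device deficiencies with the potential for a serious event follow the serious event process (8.2.4), and FDA device reporting is separate (8.2.3). A reader might infer that these AEs go unreported; the documents do not support that. Only the section 10 listing is affected.
- **A line listing cannot be biased.** This largely stands. Section 10.8 plans no rate, comparison or test, so no estimate changes. The remaining harm is an incomplete listing.
- **The word *including* in 10.8 need not mean only.** Read alone, 10.8 could cover more than ITT. Section 10.2 settles it by assigning all safety analyses to ITT.
- **The resting SpO2 condition is not a stated exclusion.** This stands. The rest has no upper limit, and Mobi is titrated to the same 90% threshold. A reader might infer that the plan removes anyone below it, but the text does not say so.
- **Eligibility is settled at screening.** Section 7.2 randomizes only eligible participants, and 10.2 does not say whether eligibility can be reassessed later. This half of the gap arises only if it can. It would then be a deviation case, though the participant could have used both devices.
- **The rest before the walk is not Mobi exposure.** This stands as far as it goes. Participants rest on their supplemental oxygen device, which is not stated to be Mobi. The exposure at issue is titration and any later use of a study device, not the rest itself.

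**Conclusion.** The concern holds as a minor defect of definition. As written, 10.2 and 10.8 can leave recorded AEs of exposed participants out of the only safety output planned in section 10. This rests on reading 10.2 as governing 10.8. For the second group, it also rests on eligibility being open to judgment after device use.

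Few participants are likely to be involved, in a single-visit study of 32 with a device that section 9.1.1 describes as FDA-cleared and assesses as non-significant risk. The primary analysis and the sample size are unaffected.

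A reader might want to use the plan's 5% drop-out allowance to size the gap, which would give 32 × 0.05 = 1.6 participants. The documents do not support that use. Section 10.4 ties the 5% to both treatments being completed in one visit and does not split it by stage. The partial completion that 10.2 describes is a participant who finishes the first walk but not the second, and that participant stays in ITT and in the listing.

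**What to change.** In 10.2, define a safety population of all participants exposed to either study device, including during Mobi titration, regardless of eligibility and of whether a walk was started. Name this population in place of ITT for all safety analyses in 10.2 and for the AE listing in 10.8. Leave the ITT and Completed Cases definitions as they are for the efficacy analyses.

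The cost is a change of wording in two sections and possibly a few more listed events. It needs no new data, because the AEs are already collected on everyone, and it changes neither the sample size nor the primary analysis.

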#### 7.1.7 Oxygen prescription 

- Long-term oxygen therapy history
- POC use history
- Normal practice with oxygen use during ambulation/exertion

Participants meeting all of the inclusion criteria and none of the exclusion criteria are qualified to enroll in this study. A qualified participant can continue to Visit 1 immediately, or return to the investigational site within 7 days.

## 7.2 Visit 1

Eligible participants will be randomized into one of two study groups, which will define the order in which they use the control device or Mobi™ device during the 6MWT. The overall Visit 1 procedure is presented graphically in Figure 7-1:

[figure not shown]

Figure 7-1

The order of 6MWTs will be randomized within the EDC, and in each of the two 6MWTs the participants will use either:

- Mobi™; or
- A portable oxygen cylinder.

Site staff will pull the oxygen cylinder via a trolley or carry the Mobi™ device via its carrying bag. This will ensure consistency across tests. 6MWTs will be conducted according to current ERS/ATS field test guidelines.

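### The ITT set in 10.2 leaves out randomised participants who do not begin the first walk, and the only check on the completers analysis assumes data missing at random

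*Combined protocol and SAP*

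**What the plan says.** Section 10.2 defines two sets. ITT is "all patients who meet the inclusion/exclusion criteria and begin the first 6MWT". Completed cases (CC) are "all patients in the ITT population who complete both the first and second 6MWTs". It then assigns the analyses:

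- Primary: "The primary endpoint analysis will be based on the CC participant population". The secondary endpoints also use CC.
- Sensitivity: "A sensitivity analysis of the primary endpoint will be generated for the ITT population". Section 10.9 specifies a maximum-likelihood mixed model that is appropriate under missing at random (MAR).
- Safety: "All safety analyses will be generated for participants in the ITT population". Section 10.8 repeats this for the adverse event listing.

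The events before the first walk are described in Section 7. Under Visit 1 (7.2), "Eligible participants will be randomized into one of two study groups". Section 7.2.1.1 follows: "Each participant will undergo titration using Mobi", with a target SpO2 of at least 90%. It also requires a resting SpO2 of at least 90% "prior to starting each 6MWT". The resting value follows at least an hour on the participant's supplemental oxygen device. The cylinder walk uses the original prescription, and the Mobi walk uses the titrated setting. No eligibility criterion in 6.2 or 6.3 requires a successful Mobi titration.

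**The concern.** An ITT set normally starts from randomisation. This one starts from beginning the first walk, and two SpO2 steps come before that point: titration on the test device, and the resting requirement. If a participant does not begin because 90% was not reached on a device, the exclusion is related to that device. It may also depend on sequence, because the same failure could keep a participant out of ITT when that device comes first and leave them in ITT when it comes second.

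Two things are at stake. First, the primary non-inferiority analysis uses completers only, and its one check is drawn from a set that may already have lost participants for device-related reasons. That check also relies on MAR for the missing walks it does contain. In a non-inferiority trial, losing poor Mobi results favours the claim. Second, every participant is to be exposed to Mobi at titration, yet an adverse event at titration that prevents the first walk falls outside the planned listing.

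**Working it through.** **1. Who is in which analysis, from 10.2, 10.8 and 10.9.**

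| Participant | CC (primary, secondary) | ITT sensitivity | Safety listing |
|---|---|---|---|
| Titrated on Mobi, does not begin walk 1 | no | no | no |
| Cylinder first, walks, then no Mobi walk | no | yes, cylinder value only | yes |
| Mobi first, begins, then stops completely | no | yes | yes |
| Completes both walks | yes | yes | yes |

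Only the first row is absent everywhere.

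**2. What MAR does with the second row.** The participant contributes a cylinder value and no Mobi value. With the planning figures in 10.4 (r = 0.2, concentrator SD 3.5), a cylinder value one SD below average predicts a Mobi value only 0.2 × 3.5 = 0.7 points below the Mobi average. The model therefore treats this person as close to an average Mobi performer, even if the walk is missing because Mobi failed.

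**3. The plan's own figures (10.4).**

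- SD of the difference = √(3.5² + 2.2² − 2 × 0.2 × 3.5 × 2.2) = √14.01 = 3.74, as stated.
- Power from the noncentral t (df = n − 2, margin 2, true difference 0, one-sided 0.025) is 79.3% at n = 29 and 80.7% at n = 30. The stated 30 is reproduced.
- 30 / 0.95 = 31.6, rounded up to 32, as stated.

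**4. Illustration of the size.** Taken from the documents: 32 randomised, margin 2, SD 3.74, one-sided 0.025. Assumed, with no figure in the documents: k participants are left out, each with a Mobi-minus-cylinder difference D. Let the true mean over all 32 be exactly −2, so that a non-inferiority claim would be false.

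Mean among those analysed = (−2 × 32 − kD) / (32 − k)

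The chance of declaring non-inferiority comes from the noncentral t with n = 32 − k, df = n − 2 and noncentrality (2 + that mean) × √n / 3.74.

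| k | D | Mean among those analysed | False non-inferiority |
|---|---|---|---|
| 0 | – | −2 | 2.5% |
| 1 | −6 | −58/31 = −1.871 | 3.8% |
| 1 | −10 | −54/31 = −1.742 | 5.6% |
| 2 | −6 | −52/30 = −1.733 | 5.7% |
| 2 | −10 | −44/30 = −1.467 | 11.4% |

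For scale, the planned 5% dropout is 0.05 × 32 = 1.6 participants from all causes.

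**The case against.** A reader might infer that participants in whom Mobi fails vanish from every analysis. The documents do not support that. The second and third rows of the first table remain in ITT and in the safety listing, and are lost only from CC.

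A reader might also infer that anyone whom Mobi cannot bring to 90% is barred from walking. No section says so. For titration, 90% is a target with no stated consequence if it is missed. The explicit condition is the resting value, and 7.2.1.1 and 7.2.3 describe the rest as being on the participant's supplemental oxygen device. If that is the usual device, someone who failed Mobi titration could still begin a walk. If it is the test device, a cylinder-first participant could still begin on the cylinder.

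Three further objections stand:

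- Randomisation before titration is implied by section order only. The Visit 1 figure, which may settle it, is not shown in the available text. If titration came first, those failing it would not be randomised participants. Selection on Mobi response would remain, and so would the gap in the adverse event listing.
- The bias need not run one way. The resting requirement also precedes the cylinder walk, and the cylinder is set to the original prescription. A cylinder-first participant who failed on the cylinder could also be left out, which would work against Mobi.
- Redefining ITT alone would not change the sensitivity estimate, because a participant with no walk data contributes nothing to the likelihood. Only the added analysis can change it.

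On safety, 8.2.1 collects adverse events on all participants. The gap is therefore in the planned listing, not in data collection.

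**Conclusion.** The point holds in a limited form. The set called ITT is not all randomised participants, and all planned outcome and safety analyses sit inside it. A randomised participant exposed to Mobi at titration who does not begin the first walk is in none of them. Whether such an exclusion would be device-related or depend on sequence cannot be settled from the text, which does not state what follows a failed titration or on which device the resting check is made, and only implies when titration takes place relative to randomisation. Separately, for participants who stay in ITT without a Mobi walk, the MAR model is a weak check when Mobi failure caused the gap. The completers-only result therefore lacks an adequate check.

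The error rates of 3.8% to 5.6% (one left out) and 5.7% to 11.4% (two left out) show what a small loss could do. They rest wholly on the assumed number and differences, and on losses being confined to poor Mobi performers. They do not predict what will happen in this trial, and no figure in the plan is contradicted.

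**What to change.** - **10.2:** define ITT as all randomised participants, or rename the present set modified ITT.
- **10.8:** base the adverse event listing on everyone exposed to a study device, including at titration.
- **10.9:** add a sensitivity analysis that counts a Mobi walk not started or not completed for a device-related reason as unfavourable to Mobi (for example, the worst observed paired difference), with a tipping-point table.
- **Reporting:** next to the primary result, give the number not reaching the SpO2 requirement and the number not starting or not completing a walk, by device, sequence and reason.
- **Population:** if the intended population is only those who reach 90% on Mobi, say so and limit the conclusion to them.
- **7.2, 7.2.1.1 and 7.2.3:** the sponsor should reconcile these on the order of randomisation and titration and on the device used for the resting check. What is done clinically after a failed titration is for the sponsor to specify.

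The cost is SAP wording, one sensitivity table and one count table. The planned 30 evaluable and 32 randomised are unchanged, and no procedure is added. The downside is a few imputed values and a slightly less favourable sensitivity result.
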